10.4 Responsibilities

Principal Investigator (PI):

- Attendance at the initiation meeting/teleconference.
- Training of new members of the trial team in the protocol and its procedures.
- Ensuring that the ISF is accurately maintained.
- Dissemination of important safety or trial-related information to all stakeholders at their site.
- Checking for AEs and ARs when participants attend for treatment / follow-up.
- Ensuring that AEs are recorded and reported in line with the requirements of the protocol.
- Ensuring that all SAEs are recorded and reported to the Sponsor within 24 hours of becoming aware of the event, and providing further follow-up information as soon as available.
- Using medical judgement in assigning seriousness, causality, and severity of SAEs.
- Providing an opinion on the expectedness of an SAE with reference to the trial protocol and Reference Safety Information.
- Using definitions in this protocol, flagging events of special interest or potential endpoints.

Chief Investigator (CI)

- Providing clinical oversight of the safety of patients participating in the trial, including an ongoing review of the risk/benefit.
- Providing clinical review of section 4.8 of the representative SmPCs on an annual basis to define the Reference Safety Information for the trial.
- Using medical judgement to confirm seriousness and causality of all SAEs.
- Reviewing expectedness of related SAEs with reference to the trial protocol and Reference Safety Information.
- Preparing the clinical sections and final sign-off of the Development Safety Update Report (DSUR).
- Using definitions in this protocol, confirming events of special interest or potential endpoints.

Sponsor:

- Central data collection and verification of AEs, SAEs, SARs and SUSARs according to the trial protocol.
- Maintaining the Reference Safety Information for the trial and ensuring it is complies with regulatory guidance.
- In the absence of the CI and their delegates, reviewing expectedness of SAEs against the Reference Safety Information.
- Reporting safety information to the CI or delegate for the ongoing assessment of risk/benefit.
- Reporting safety information to the independent oversight committees identified for the trial (Independent Data Monitoring Committee (IDMC) and/or Trial Steering Committee (TSC)) according to the Trial Monitoring Plan.

Version 5.0 22 July 2021 Page 57 of 82

- Expedited reporting of SUSARs to the Competent Authority (MHRA in UK) and REC within required timelines.
- Notifying Investigators of SUSARs that occur within the trial.
- Annual checking for updates to the Reference Safety Information for the trial, and notifying PIs
 of any changes.
- Preparing standard tables and other relevant information for the DSUR in collaboration with the CI and ensuring timely submission to the MHRA and REC.

Trial Steering Committee:

Periodically reviewing recruitment and the overall progress of the trial and liaising with the IDMC and sponsor regarding safety issues. Reporting the results of the trial to the investigators and wider public and writing primary and secondary papers.

Trial Management Group:

They will be responsible for day to day running of the trial.

Independent Data Monitoring Committee:

In accordance with the Charter for the IDMC, periodically reviewing unblinded safety data in individual cases and to determine patterns and trends of events, or to identify safety issues, which would not be apparent on an individual case basis, reporting concerns to the TSC and sponsor.

Clinical Endpoint Committee (CEC):

In accordance with the Charter for the CEC, review and classify all potential clinical endpoints in the trial.

10.5 Notification of deaths

All deaths occurring within the trial will be reported within the eCRF as an SAE.

10.6 Pregnancy reporting

Women at risk of pregnancy are excluded from this trial. Patiromer is not absorbed and therefore is not considered a risk to female partners of male participants. MRA are guideline-recommended therapy and are not known to pose a risk to female partners of men who take MRA.

10.7 Overdose

Patients may take an overdose of patiromer or MRA deliberately or inadvertently.

Definition: An overdose is defined as a patient who has taken substantially more of the IMP than intended, either in a single large dose (usually this will be a deliberate act of self-harm) or a smaller deviation but over a longer period of time. For this protocol, the latter will be defined as taking a dose-level higher than intended that either persists for more than one month or results in hospitalisation or death.

Overdoses resulting in an SAE will be recorded on the SAE eCRF.

Investigators will evaluate whether it is safe for the patient to continue on IMP and if not they will revert to standard care. They will continue to be followed-up as intended in all other respects.

Version 5.0 22 July 2021 Page 58 of 82

Psychiatric advice will be sought for patients who have attempted self-harm.

10.8 Reporting urgent safety measures

If any urgent safety measures are taken the CI/Sponsor will phone the MHRA's Clinical Trial Unit on [name], ideally within 24 hours. This will be followed up no later than 3 days from the date the measures are taken, giving written notice to the MHRA (who will advise the format required) and the relevant REC of the measures taken and the circumstances giving rise to those measures. A substantial amendment must also be submitted to the MHRA.

10.9 The type and duration of the follow-up of participants after adverse reactions.

Adverse events and reactions will be recorded, reported and followed to completion in line with this protocol until 30 days after participant's last dose of the IMP.

Any SUSAR identified will be reported to the Sponsor and to the Regulatory Authorities irrespective of how long after IMP administration the reaction has occurred.

10.10 Development safety update reports (DSURs)

DSURs will be submitted within 60 days of the anniversary of the issue of the Clinical Trials Authorisation for the trial. DSURs will be prepared and submitted by the sponsor (PV Office) in liaison with the CI.

11. STATISTICS AND DATA ANALYSIS

11.1 Sample size calculation

The anticipated primary endpoint rate in the control group is 40%. We estimate that 999 subjects per group (yielding 719 first-events) will provide >90% power to detect a hazard ratio of 0.75 (25% reduction) at the 1% significance level and >80% power to detect a hazard ratio of 0.80 at the 5% significance level, which we believe reflect clinically meaningful benefit. This is based on a time to first event analysis using the Wald statistic in a Cox proportional hazards model. To allow for some uncertainty the trial will be stopped once 750 patients have experienced a primary endpoint. As the primary endpoint is a recurrent-event analysis, the trial should have additional power.

The primary endpoint at 60 days is a novel scoring system and therefore there are no prior data upon which to base assumptions. Assuming a normal distribution of "Congestion Index" scores, 400 patients provides >90% power to demonstrate a difference between strategies of 0.325 of a standard deviation in the effect size for the change in score between baseline and follow-up.

11.2 Anticipated recruitment rate

On average, the 100 sites participating in this trial will care for about 20,000 patients with advanced heart failure per year, of which we estimate 25% would be suitable and 10% would be both suitable and willing to participate in this trial. Accordingly, we anticipate that each site should be able to enrol 20 patients per year. We anticipate it will take 12-18 months to initiate all 100 sites and that not all sites will perform to target. Therefore, we assume that enrolment will take two to three years.

Version 5.0 22 July 2021 Page 59 of 82

11.3 Statistical analysis

The primary analysis will be done on the intention-to-treat population. The primary endpoint is the composite of time to need for IV diuretics (subsequent to initial discharge) for worsening or recalcitrant heart failure, hospitalisation for worsening heart failure or non-cancer deaths analysed as a recurrent event. This is a novel trial endpoint and methodology for analysing such outcomes is evolving. Therefore the methods used to analyse the recurrent events will be updated based on this evolving area of research and will be finalized prior to database lock.

Time to first event outcomes will be analysed using Cox proportional hazards models with randomised treatment as a covariate. Statistical significance will be assessed using the Walk statistic and estimated hazard ratios for the treatment effect and their 95% confidence intervals calculated.

Time to event curves will be constructed using cumulative incidence functions adjusting for competing risks where appropriate. Outcomes from the Quality of Life and congestion scores will be analysed at the specified time points using t-tests with no imputation for missing data. Days dead or hospitalised and quality-adjusted days alive and out of hospital will be analysed using re-randomisation tests adjusting for potential length of follow-up. Serious adverse events will be tabulated by system organ class and preferred term. A complete statistical analysis plan will be completed and signed off before database lock.

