1. BACKGROUND

Poor control of congestion is one of the most important unmet needs for patients with heart failure (1). Congestion is an important cause of symptoms, disability and recurrent hospitalisation that commonly results in death due to heart failure, respiratory infection or multiple organ failure.

About half of all hospital admissions with a primary diagnosis of heart failure present with peripheral oedema (>50,000 per year in the UK) (2), usually associated with orthopnoea and dyspnoea on minimal exertion (although often not at rest when sitting upright). The underlying pathophysiology in these cases is fluid retention that has developed over days or weeks (3, 4). It is perhaps misleading to use the term "acute" heart failure in such cases, which implies a medical emergency requiring a response within minutes. The term "subacute" heart failure may better convey the status of such patients, for whom a response time measured in days or weeks is appropriate. Indeed, there is growing interest in managing such patients with home-based subcutaneous furosemide or day-care 'furosemide lounges' (5). Although the presentation of "sub-acute" heart failure is less dramatic than for acute pulmonary oedema, patients with sub-acute congestion typically have longer hospital stays (in excess of 10 days) and a poorer prognosis, perhaps reflecting more advanced "right heart" dysfunction and organ congestion (1, 6). Hepatic congestion, which impairs the degradation of aldosterone, and renal congestion both exacerbate sodium retention and congestion.

Although many studies of acute heart failure have been conducted, these have focussed on emergency treatment of breathless patients rather than the management of subacute worsening of congestion. *Few substantial studies focussing on patients with worsening congestion and peripheral oedema have been published.* The CARRESS study of ultrafiltration conducted in the USA is perhaps the closest precedent. It failed to show that ultrafiltration was superior to high-dose intra-venous furosemide. By 60 days, almost 40% of patients had died or been re-hospitalised for heart failure (mortality was 15%) (7). A sub-group analysis of the RELAX-AHF trial (6) suggested that 15% of those with moderate/severe oedema would die or be re-admitted for heart failure by 60 days (mortality was about 6%).

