4.6 Other Primary Endpoints

For The Registry

Time to first (re-)hospitalisation or death

Randomised Trial until Day 60

- Congestion Index on Day 60, comprising changes from baseline in
 - i. Weight
 - ii. Severity of peripheral pitting oedema
 - iii. Breathlessness symptom score
 - iv. Dose of loop and thiazide diuretics
 - v. Walk Test Time (will be considered zero at baseline if not available)
 - vi. Plasma concentration of NT-proBNP
 - vii. Plasma concentration of CA125

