8.11 End of trial

The overall trial will be deemed complete once 750 patients have experienced a first-event. At that time, an end of trial date will be declared and investigators will be asked to contact all patients on or after that date for a final trial evaluation.

Version 5.0 22 July 2021 Page 43 of 82

The 60-day outcome will be assessed after 400 patients have had their 60-day evaluation. It is anticipated that database lock will occur within three months and that these data will be analysed and presented during the course of the main trial.

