11.6 Participant population

Analyses will be carried out on an intention to treat basis according to randomised treatment.

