11.7 Procedure(s) to account for missing or spurious data

The main analyses will be based on morbidity/mortality data for which imputation is not necessary. For quality of life outcomes, laboratory results or other continuous variables results will be analysed with and without imputation. Multiple imputation procedures will be used. Full details will be provided in the statistical analysis plan.

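### The Day-60 Congestion Index and quality-of-life t-tests compare survivors only, with no rule for death before Day 60, and the two missing-data statements conflict

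*Protocol*

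**What the plan says.** - **Endpoint.** Protocol 4.6 lists, as an other primary endpoint, "Congestion Index on Day 60, comprising changes from baseline in" seven components. The only fill-in rule is a zero for a baseline walk test that is not available. No score or rank is given for a patient who has died.
- **Test.** Protocol 11.3: quality-of-life and "congestion scores will be analysed at the specified time points using t-tests with no imputation for missing data".
- **Who is analysed.** Protocol 8.11: "The 60-day outcome will be assessed after 400 patients have had their 60-day evaluation". The Trial Summary, the table in 4.9 and the interim analysis in 11.5 also describe the 400 as patients who have completed or been evaluated at 60 days.
- **Population.** Protocol 11.6: "Analyses will be carried out on an intention to treat basis according to randomised treatment". Section 11.3 says the same of the primary analysis.
- **Missing data.** Protocol 11.7 says that quality of life, laboratory results and "other continuous variables results will be analysed with and without imputation", and then "Multiple imputation procedures will be used". Death is not mentioned, and the details are left to the SAP.
- **Use.** Under 11.5, no significant difference in the index or in NT-proBNP at 60 days counts as lack of improvement in congestion, one of two grounds for asking the IDMC to consider stopping.
- **SAP.** Sections 1.6.1 and 1.6.3 report early closure with four participants randomised and no formal analysis.

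**The concern.** A change from baseline to Day 60 does not exist for someone who died on Day 30. With no imputation, that patient leaves the t-test, and no sentence brings the patient back. What remains is a comparison of patients selected by surviving, and survival is something the strategy is meant to change. The Background also allows that higher MRA doses might be unsafe without close monitoring.

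The direction of the error is the problem. If one arm loses more of its sickest patients, its survivors look less congested and the index credits that arm. If an arm keeps its sickest patients alive, the index counts against it. Multiple imputation under 11.7 would not settle this: applied to patients who died, it would assign a Day-60 score as though they were alive.

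**Working it through.** **1. The plan's own power.** Inputs from Protocol 11.1: 400 patients, 0.325 SD. Allocation is 1:1 (8.4). The Day-60 significance level is not stated; two-sided 5% is assumed.

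Power = Φ(d√(n/2) − 1.96) = Φ(0.325 × √100 − 1.96) = Φ(1.29) = 90.1% (noncentral t: 90.0%). This reproduces the stated figure. Two-sided 1% would give 75.0% and one-sided 5% would give 94.6%.

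**2. Whether deaths reduce that power.** The 400 are completers, so as written they do not. Reaching 400 survivors with scores needs more randomised patients: 400/0.94 = 426 at 6% mortality and 400/0.85 = 471 at 15%.

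**3. Survivor bias.** The mortality inputs come from the Background: 15% at 60 days in a cited ultrafiltration trial, and about 6% in a subgroup with moderate or severe oedema from a cited acute heart failure trial. The differences between arms and the correlation ρ are assumptions.

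Let the index have SD 1 (higher = more congested) and correlation ρ with a normal death risk. The patients above c = Φ⁻¹(1 − m) die, where m is mortality. The survivors' mean is −ρλ(m), with λ(m) = φ(c)/(1 − m). With no effect on the underlying score, the expected difference (patiromer minus control) is ρ[λ(control) − λ(patiromer)]; a positive value makes patiromer look worse.

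| Control v patiromer mortality | λ control | λ patiromer | ρ = 0.3 | ρ = 0.7 |
|---|---|---|---|---|
| 15% v 11.25% | 0.2743 | 0.2153 | +0.018 | +0.041 |
| 15% v 10% | 0.2743 | 0.1950 | +0.024 | +0.056 |
| 15% v 20% | 0.2743 | 0.3500 | −0.023 | −0.053 |
| 6% v 4.5% | 0.1267 | 0.0993 | +0.008 | +0.019 |
| 6% v 9% | 0.1267 | 0.1785 | −0.016 | −0.036 |

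The size runs from 0.008 to 0.056 SD. The largest is 0.056/0.325 = 17% of the target difference. Harsher assumptions (control mortality 15%, halved or raised by half, ρ = 0.8) give 0.097 and 0.090 SD.

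**4. Effect on the test.** Simulation with 200 randomised per arm, 3,000 runs, ρ = 0.5 and no effect on the underlying score. The entries show how often each test significantly favours patiromer (nominal 2.5%).

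| Control v patiromer mortality | Survivor t-test | Death ranked worst (Wilcoxon) |
|---|---|---|
| 15% v 15% | 2.6% | 2.6% |
| 15% v 22.5% | 7.6% | 0.1% |
| 15% v 7.5% | 0.5% | 12.1% |

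With equal mortality there is no material bias. With unequal mortality the survivor test moves the wrong way.

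**5. Price of ranking death worst as the main test.** With 400 randomised, a true 0.325 SD effect and equal mortality, its power is about 82% at 6% mortality and about 67% at 15%.

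**The case against.** No sentence says that deaths are excluded. Section 11.7 can be read as a main analysis plus a sensitivity analysis, with details deferred. Early deaths are counted elsewhere: days dead or in hospital to Day 60 is a secondary endpoint with its own re-randomisation test, and non-cancer deaths are in the long-term primary composite. The IDMC sees unblinded serious adverse events, and every death is reported as one (10.5). The bias is small and vanishes if mortality is equal.

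Most of this stands and limits the size of the point. It does not remove it: exclusion is what 11.3 produces when applied, the other endpoints do not correct the index, and neither reading of 11.7 supplies a rule for death.

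Three stronger readings are tempting and should not be drawn:

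- **That deaths cut the stated power.** Counting 400 as randomised leaves 376 or 340 scores and power of about 88% or 85%. The protocol defines the 400 as completers, so these figures do not apply.
- **That one missing component voids the index.** No rule for combining the components or handling a missing one is given, so any power loss from this would rest on an invented rule.
- **That the index alone decides futility.** Section 11.5 also tests MRA dose and names NT-proBNP. The IDMC is only asked to consider stopping, with exceptions for conditional power above 70% and for a strong trend in morbidity and mortality.

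**Conclusion.** The concern holds as a flaw in the protocol's design. As written, the Day-60 index and quality-of-life comparisons are survivor-only, which does not fit the intention-to-treat statements, and 11.3 and 11.7 give different missing-data rules, neither covering death. The likely bias is about 0.01 to 0.06 SD against 0.325 SD. That range rests on mortality of 6% to 15%, on the differences between arms in the table (a quarter to a third at 15%, a quarter to a half at 6%), and on a correlation of 0.3 to 0.7. The documents give none of the between-arm differences or correlations.

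A reader might infer that the trial's results are compromised. They are not: with four participants randomised and only summaries and listings planned, neither this t-test nor the 400-patient look will take place. The point matters for the protocol as a design and for any trial that reuses it.

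**What to change.** 1. Define the Day-60 cohort by randomisation: consecutive randomised patients who have reached the end of the Day-60 window or died, continuing until 400 have scores. This keeps the stated power. State one window, since 4.2 gives ±10 days and 8.1 gives ±14.
2. Keep the t-test, labelled as a comparison among survivors.
3. Add a pre-specified analysis that ranks death before Day 60 worst and reports a win probability, for the index and for KCCQ and EQ5D. Give it to the IDMC beside the t-test at the 400-patient futility look.
4. Limit multiple imputation to survivors with missing data.
5. Make 11.3 and 11.7 say the same thing.

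The cost is wording and one extra analysis. Making the worst-rank analysis the main test would cost more: its lower power (step 5 of the working) would have to be stated and the sample size reconsidered, although a mortality benefit would recover some of the loss.

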11.4 Subgroup analyses

The primary outcome will be analysed in the following sub-groups:

- Age (by tertile)
- Sex (categorical)
- Recruitment as an in-patient or out-patient (categorical)
- MRA dose prior to inclusion (<25mg, 25mg, >25mg of spironolactone or eplerenone)
- Systolic blood pressure (by tertile)
- eGFR (by tertile)
- LVEF (<40%, 40-49%, >49%)
- COPD (categorical)
- Diabetes mellitus (categorical)

Results will be presented within each subgroup along with a test for treatment by subgroup interaction.

11.5 Interim analysis and criteria for the premature termination of the trial

Unblinded trial data will be reviewed on an ongoing basis by the IDMC. The primary role of the IDMC will be to protect the interests of the patients. The IDMC may recommend to the TSC and Co-Sponsors that the trial should be stopped prematurely because of concerns about patient safety of conclusive evidence of overwhelming benefit. The IDMC will meet after 100, 200, 400, 1,000, 1,500 and 2,000 patients have completed 60-day follow-up.

The IDMC may recommend stopping the study for safety at any time. At each meeting, the IDMC will review the overall rate of serious adverse events and serious adverse events of special interest (hypokalaemia, hypotension, renal failure, arrhythmias and heart failure) that may be influenced (favourably or unfavourably) by intervention.

The IDMC will take into account all results and the consistency and biological plausibility of the findings in making any recommendation. The final decision on continuing or stopping the trial will lie with the TSC/Co-Sponsors. The pre-specified stopping guidelines below will be detailed in the IDMC Charter and statistical analysis plan.

Version 5.0 22 July 2021 Page 60 of 82

Interim analysis

If the analysis of 60-day outcome for the first 400 patients evaluated at 60 days suggests a potential failure of the treatment strategy [either similar doses of MRA amongst patients assigned to patiromer and standard care or a lack of improvement in congestion by Day-60] then the IDMC will be asked to consider stopping the trial unless the conditional power of the trial to show benefit on the primary endpoint exceeds 70%.

- In order for the dose of MRA to be considered dissimilar for participants assigned to patiromer compared to standard care the following criteria should be met:-
 - The mean dose of MRA of those assigned to patiromer should be >50% higher (i.e. 25mg/day versus >37.5mg/day) than for those assigned to standard care.
 - o This difference should be statistically significant
- If there is no significant difference in either the overall congestion index or in plasma concentration of NT-proBNP at 60-days, then this will be considered a lack of improvement in congestion.

If patiromer fails by either or both criteria, the trial may be terminated unless a strong trend to benefit on morbidity and mortality is observed in the overall trial data. At the time of this evaluation, we anticipate that >100 patients will have been followed for at least one year, up to 800 patients may have been randomised altogether and >200 primary endpoints will have occurred.

